## Study Description

Rebound pain is a well-recognized phenomenon after the resolution of peripheral nerve blocks. (1–5) Severe rebound pain is prevalent after ambulatory surgery, with potential resultant increased health-care utilization and cost. (6) Risk factors for severe rebound pain may include younger age, female sex, high preoperative pain score, bone surgeries, and upper limb surgeries. (7–10) Use of tourniquet for lower limb procedures is also associated with worse postoperative pain compared to without. (11,12) Protective factors may include continuous perineural catheter, regional anesthesia adjuncts, and multimodal oral pain management prior to resolution of peripheral nerve blockade. (8,9,13–17) However, placement of continuous peripheral nerve block catheters utilizes additional health care resources; hence, a targeted approach where continuous perineural catheters are offered to patients at the highest risk of severe rebound pain could potentially offer the biggest benefit. The aim of the study is to derive and validate a multivariable prediction model for severe rebound pain after lower limb surgery involving popliteal blockade, to assist with risk stratification and shared decision making.

## Primary Objectives

The primary objective of the study is to derive and validate a multivariable clinical prediction model to predict the risk of severe pain after lower limb orthopedic surgeries after single-shot popliteal sciatic nerve blocks resolution.

## Data Source

The St. Paul's Hospital Peripheral Nerve Block (PNB) Database (in REDCap) will be used.

## Study Sample

### *Inclusion*

Patients undergoing lower limb surgery who received single-shot popliteal sciatic nerve blocks (with or without other peripheral nerve blocks) at St. Paul's Hospital, Vancouver, from January 4, 2016 to November 1, 2019 will be included.

### *Exclusion*

For patients who had multiple surgeries during the study period, only the first surgery within the study period will be selected. Patients who had uncontrolled pain (defined as NRS >3 and/or nursing note documentation of uncontrolled or severe pain and/or undocumented pain status) in the recovery room will also be excluded as this consists of a heterogeneous group of patients who may have had failed block or experience pain from sites away from the blocked area, neither of which may be helped by continuous peripheral nerve block catheters. Patients receiving popliteal sciatic nerve catheters will be excluded.

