## Model Endpoints

The primary endpoint is severe rebound pain, defined by transition from well-controlled pain (numerical rating scale [NRS] 3 or less or patient report of satisfactory pain control) in PACU while the block is working to severe pain (NRS pain score 7 or greater) within 48 h of block

performance. This definition is modified from that of Barry et al., as clinically we have noted some patients having sensory blocks lasting more than 24 hours with the use of adjuncts.

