### **Additional cohort characteristics to be reported:**

- Pre-PNB neuropathy (Present or absent; Defined as “Yes” for either Pre-PNB neuropathy or diabetic neuropathy)
- Tourniquet location (Leg versus thigh)
- Tourniquet duration
- Block performer (Attending/ Fellow/ Resident)
- Duration of sensory blockade (as defined by time from PNB performance to return of normal sensation) (Continuous variable);
- Duration of motor blockade (As defined by time from PNB performance to return of normal movement) (Continuous variable);

- Time of day the nerve block wore off (Between 0000- 0700 / Between 0701-2359) (25,26)
- Health care practitioner contact, as defined by answering “yes” to the question of “Did you have to visit the emergency department, or call the surgeon or your family doctor for pain control after your nerve block wore off?”.
- Highest pain score (HPS), as defined by the highest NRS pain score upon resolution of peripheral nerve blockade within 48 hours of block performance.

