### **Model building**

Correlations amongst candidate predictors will be explored to avoid risks of collinearity (for example, between dexamethasone use and type of intraoperative anesthesia). Amongst multiple highly correlated predictors, only one will be selected for the modeling based on clinical reasoning (e.g. one variable is more easily collected, less missing values, etc.). Additionally, potential multicollinearity within the final model will be diagnosed using variance inflation factors (VIF) of the predictors, with any values exceeding 4 warranting further investigation.

Multivariable logistic regression will be the statistical method used to construct a prediction model, with the above outlined imputation procedure applied to the data prior to modelling. The prediction model will contain the complete variable set as predictors (as outlined in the Candidate Predictors section). “Age”, the only continuous predictor to be included in the model, will be modelled with a natural cubic spline (with 3 interior knots).

In addition, an exploratory prediction model will be created where a natural cubic spline (with 3 interior knots) will also be fitted for an additional predictor of “Tourniquet duration”. This serves as an exploration of whether tourniquet duration plays a predictive role. However, this exploratory model could only be used postoperatively, when this information becomes available. Future database with information on predicted tourniquet duration would be needed for model update to minimize bias if this predictor were to be applied preoperatively. The primary and exploratory models will then be compared in terms of predictive performance and a likelihood ratio test will also be conducted to assess differences in goodness-of-fit.

To assess the performance of the predictive models, we will proceed with a bootstrap validation approach with 100 repetitions. At each repetition, the data will be sampled with replacement to form a bootstrap sample (with sample size equivalent to the original dataset). Multiple imputation will then be conducted on the bootstrap sample prior to modelling (using the same procedure outlined in the above “Missing values” section). After the pooled bootstrap model is created for the given bootstrap sample, performance measures (as discussed below) will be pooled across the 10 multiply imputed datasets of (1) the bootstrap sample and (2) the original

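### Does restricting the model to patients with controlled recovery-room pain undermine its use for a catheter choice made before surgery?

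*Combined protocol and SAP*

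**What the plan says.** The Study Description gives the purpose as a targeted approach in which "continuous perineural catheters are offered to patients at the highest risk of severe rebound pain", with a model "to assist with risk stratification and shared decision making". Primary Objectives states the aim as "to predict the risk of severe pain after lower limb orthopedic surgeries after single-shot popliteal sciatic nerve blocks resolution", with no recovery-room condition.

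Exclusion removes patients with recovery-room NRS above 3 "and/or nursing note documentation of uncontrolled or severe pain and/or undocumented pain status) in the recovery room will also be excluded". It gives the reason: such patients may have a failed block or pain away from the blocked area, "neither of which may be helped by continuous peripheral nerve block catheters". Patients who received catheters are also excluded.

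Model Endpoints defines severe rebound pain as a change from well-controlled pain ("numerical rating scale [NRS] 3 or less or patient report of satisfactory pain control") in PACU, with the block working, to NRS 7 or more within 48 h of the block. The additional cohort characteristics include a highest pain score, defined as "the highest NRS pain score upon resolution of peripheral nerve blockade within 48 hours of block performance".

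Model building says of the tourniquet model only that "this exploratory model could only be used postoperatively, when this information becomes available". The bootstrap, calibration, decision curve and points system name no population other than the study sample.

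**The concern.** No section states when the primary model is to be used. Two things suggest before surgery: the talk of offering catheters and sharing decisions, and the fact that only the tourniquet model is confined to postoperative use. At that time nobody knows whether pain will be controlled in PACU. The model therefore estimates the chance of severe pain given controlled PACU pain, while a patient facing the choice has not yet met that condition.

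Two consequences would matter if the conditioning were overlooked. First, the risk of the defined endpoint seen from before the block is c(X) times the model's value, where c(X) is the probability of controlled PACU pain for predictors X. If c(X) varies between patients, their ranking can change as well as the level of risk. Second, the decision curve leaves out the excluded patients, some of whom would have been scored and offered a catheter, so its net benefit might not carry over to all single-shot patients.

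Two smaller points add to the impression of a gap. The failed-block reason does not cover patients whose PACU status is merely undocumented. And a patient with NRS 4 who reports satisfactory control is excluded under one section but well controlled under the other.

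**Working it through.** **Inputs.** From Sample size: event rate 50%, and Cox-Snell R² of 0.1 (shrinkage criterion) or 0.2 (optimism criterion). The documents do not give the share excluded for PACU status (s), c(X), the event risk r in excluded patients, or any decision threshold t. All of these are assumed below. The plan has no figure of its own on this point to reproduce.

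**Level of risk, planned endpoint.** Pre-block risk = c × 0.50. For c = 0.95, 0.90, 0.80 this is 0.475, 0.45, 0.40. If every exclusion were for undocumented status, missing at random, c = 1 and the risk stays 0.50.

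**Ranking.** Model risks 0.50 and 0.45 with c(X) of 0.80 and 0.95 become 0.50 × 0.80 = 0.400 and 0.45 × 0.95 = 0.4275. A reversal is possible, but both c(X) values are invented.

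**Net benefit.** Take a calibrated model with a normal linear predictor centred at 0 (event rate 50%). R² = 0.1 corresponds to SD 0.703, and R² = 0.2 to SD 1.123. Let o = t/(1−t), and let q be the share flagged at t. Assume excluded patients have the same predictor distribution and a risk r unrelated to predicted risk. Then:

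- NB_excluded = q × (r − (1−r) × o)
- NB_all = (1−s) × NB_planned + s × NB_excluded
- Treat-all = p − (1−p) × o, with p = (1−s) × 0.50 + s × r
- Gain = NB − max(treat-all, 0)

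At t = 0.40 with R² = 0.1: o = 0.667, q = 0.718, NB_planned = 0.2106. Planned treat-all is 0.50 − 0.50 × 0.667 = 0.1667, so the planned gain is 0.0439. With s = 0.20:

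| Rule for excluded patients | NB_excluded | NB_all | Treat-all | Gain |
|---|---|---|---|---|
| Any NRS ≥ 7 counts, r = 90% | 0.598 | 0.2881 | 0.3000 | −0.0119 |
| Any NRS ≥ 7 counts, r = 50% | 0.120 | 0.1924 | 0.1667 | 0.0257 |
| Any NRS ≥ 7 counts, r = 30% | −0.120 | 0.1446 | 0.1000 | 0.0446 |
| Counted as non-events (r = 0) | −0.479 | 0.0728 | 0.0000 | 0.0728 |

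**Sensitivity to the assumptions.**

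- t = 0.40, R² = 0.1, s = 0.10: gain 0.0442, 0.0348, 0.0160 for r = 30%, 50%, 90%.
- t = 0.40, R² = 0.2, s = 0.20: planned gain 0.0878; all patients 0.0822, 0.0582, 0.0104 for the same r.
- t = 0.50, R² = 0.1, s = 0.20: planned gain 0.1305; all patients 0.0644, 0.1044, 0.0244 for the same r, and 0.0044 with excluded patients as non-events.

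The non-event rule raises the gain at a 40% threshold and almost removes it at 50%. Neither the direction nor the size is fixed by anything in the documents.

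**Reading the sections together.** Model performance measures describes its output as the risk of a severe rebound, and Model Endpoints defines that term as a transition from controlled PACU pain. The condition is therefore carried by the endpoint's name. Primary Objectives is looser, but pain after a block resolves presupposes a block that worked. A patient with undocumented PACU status cannot be classified on this endpoint at all. Exclusion thus follows from the endpoint, in keeping with the Missing values rule that drops observations with no outcome. The NRS 4 patient is settled by Exclusion, which decides who enters the dataset; patient report under Model Endpoints can be read as the alternative when no NRS was recorded.

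**The case for a change.** The best case for a change is that the stated reason for the exclusion does not make the excluded patients identifiable beforehand. If a catheter would not help them, those who are flagged still dilute the value of model-guided selection, and the planned decision curve does not show it. Wording and exclusion counts would cost almost nothing, and one extra analysis could reuse the planned code. A points score could otherwise be read at the bedside as an unconditional risk.

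The mismatch between the analysis population and the likely population of use stands as a limit on interpretation. The case for an added analysis is weaker, for four reasons.

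- Refitting the same predictors to any NRS 7 or more in all single-shot patients produces a new model for a new outcome. It does not measure how the planned model performs in that group.
- That outcome counts pain which, on the plan's own reasoning, a catheter may not help.
- The highest pain score is defined at block resolution, which has no clear meaning when a block failed, and the documents do not say whether excluded patients have 48 h scores.
- Catheter recipients would still be missing, so the population would remain incomplete.

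**Conclusion.** The concern describes the plan correctly, but no change follows. Conditioning on controlled PACU pain is a deliberate, disclosed trade-off: it gives a cohort in which rebound pain is defined and a catheter could plausibly help, at the price of risks that apply only once the block has worked. No stated rule or figure is shown to be wrong.

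The illustrative change in gain at a 40% threshold runs from 0.044 down to −0.012 or up to 0.073. This rests on an assumed 20% excluded, R² of 0.1, and risk in excluded patients unrelated to predicted risk. With 10% excluded or R² of 0.2, the gain at that threshold stays positive for every r from 30% to 90% examined. Preoperative use is itself an inference.

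The unconditional wording of the objective, the grouping of uncontrolled with undocumented status, and the NRS 4 case are matters of clarity that analysts can resolve sensibly from the endpoint definition and the exclusion rule. Resolving them alters no planned result.

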## Model Endpoints

The primary endpoint is severe rebound pain, defined by transition from well-controlled pain (numerical rating scale [NRS] 3 or less or patient report of satisfactory pain control) in PACU while the block is working to severe pain (NRS pain score 7 or greater) within 48 h of block

performance. This definition is modified from that of Barry et al., as clinically we have noted some patients having sensory blocks lasting more than 24 hours with the use of adjuncts.

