### **Lower Limb Candidate Predictors**

As there is currently no agreed method of classifying lower limb surgeries systematically as it pertains to postoperative pain, we reviewed the literature and consulted an orthopedic surgeon specializing in foot and ankle surgery ([name]) to categorize surgeries into a ranked list by anatomy, clinical similarity (e.g. fusion), and known risk factors of increased postoperative acute pain or rebound pain. If multiple surgeries are present, the surgery in the category that is deemed the most involved (i.e. higher ranking) will be selected as the primary surgery.

The following a-priori predictors were included:

- Patient will be assigned one main surgical type (i.e. surgery type is considered one class/categorical variable with Group 9 Soft tissue only as the reference):
  - 1= Fusion/Osteotomy of Ankle/Hindfoot/Midfoot (10,18,19)
  - 2= Total Ankle Replacement (18)
  - 3= Acute Bony Trauma (18–22)
  - 4= Hallux Valgus Surgeries (18)
  - 5= Hardware Removal (18)
  - 6= Amputations
  - 7= Other Ankle/Hindfoot/Midfoot bony procedure (19,23,24)
  - 8= Other Forefoot bony procedure (19,23,24)
  - 9= Soft tissue only (8,18)
- Other surgical predictors
  - Planned admission (Pre- or post-operatively) vs. ambulatory procedure
- Patient characteristics:
  - Age (continuous);
  - Sex (binary);
- Anesthesia-related:
  - Local anesthetic type (Long-acting only vs. mixed);
  - Dexamethasone use (Present or absent);
  - Intraoperative Anesthesia (General anesthesia as defined by need for advanced airway/Sedation/Spinal).

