#### Missing values

Any variables with >10% missing data among observations will be excluded from the modelling stage. Any variables with <10% missing data among observations will have their missing values imputed using multiple imputation.

Since the primary variable of interest “Main surgery type” has numerous categorical levels, we intend to omit any observations that are missing a “Main surgery type” value, given the greater risk of non-convergence when attempting to impute this variable. Also, any observations with missing values in the primary outcome (rebound pain scores) will be excluded too. The remaining variables are assumed to be missing at random (MAR).

The planned method of multiple imputation will be by using multivariate imputation by chained equations (MICE). The following imputation techniques will be used to impute each variable with missing data:

- “Predictive mean matching” will be used to impute the continuous variables

- Logistic regression will be used to impute the binary variables
- Multinomial logistic regression will be used to impute the nominal categorical variables

All variables (including the outcome) will contribute to imputation of the missing values. The plan of the imputation will be to generate 10 multiply imputed datasets (with an anticipated maximum of 20 iterations to achieve convergence), which will then be used to model and pool results.

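### Does the primary endpoint need rewriting because it does not repeat that severe pain must follow block resolution, and does not classify a block unresolved at 48 h?

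*Combined protocol and SAP*

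**What the plan says.** Four sections bear on how the outcome is coded.

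- **Primary Objectives:** the model predicts "severe pain after lower limb orthopedic surgeries after single-shot popliteal sciatic nerve blocks resolution".
- **Model Endpoints:** the event, named severe rebound pain, runs from controlled pain in PACU with the block working to "severe pain (NRS pain score 7 or greater) within 48 h of block" performance. The 48 h window is chosen because of "some patients having sensory blocks lasting more than 24 hours with the use of adjuncts".
- **Additional cohort characteristics to be reported:** highest pain score is "the highest NRS pain score upon resolution of peripheral nerve blockade within 48 hours of block performance". It is listed as a descriptive item, not as the endpoint.
- **Missing values:** "any observations with missing values in the primary outcome (rebound pain scores) will be excluded too".

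Dexamethasone use is the one block adjunct among the candidate predictors. Inclusion admits patients with "single-shot popliteal sciatic nerve blocks (with or without other peripheral nerve blocks").

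**The concern.** Read literally and separately, the sections can classify two kinds of patient differently.

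1. **Block unresolved at 48 h, no score of 7 or more recorded.** By the endpoint sentence this is a non-event. If the outcome were built from highest pain score, there would be no post-resolution score, and the missing-outcome rule might remove the patient.
2. **Severe pain after PACU but before the block resolves.** This meets the words of the endpoint sentence but not those of highest pain score. It could arise where other blocks were placed, or from pain outside the blocked area. The Exclusion section removes recovery-room patients partly because they may "experience pain from sites away from the blocked area, neither of which may be helped by continuous peripheral nerve block catheters".

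Both kinds become more common as blocks last longer, and adjuncts lengthen blocks. The coding rule could therefore bear unevenly on the dexamethasone coefficient and its points. Excluding unresolved blocks would also select patients on a quantity known only after baseline.

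**Working it through.** **Reading the sections together.** Study Description introduces rebound pain as something that follows the resolution of a block. Primary Objectives says the same of the outcome. Model Endpoints uses that name and sets the severe score against a PACU state in which the block works. The missing-outcome rule applies to the primary outcome, which Model Endpoints defines. No section says the endpoint is derived from highest pain score; only the phrase in parentheses in Missing values hints at a link. So a patient with pain scores recorded over 48 h and none at 7 or above has a known outcome. For kind 1, the exclusion arises only through a derivation the plan does not state.

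**The plan's own figures.** Sample size uses n = 1270, a 50% event rate and 18 parameters. Its largest requirement reproduces as exp[(-0.508 + 0.259 ln 0.5 + 0.504 ln 18 - ln 0.05)/0.544] = 1013.2. The coefficients are not in the plan, but they return its figure. Exclusions would take the sample below this requirement only above 1 - 1013.2/1270 = 20.2% of patients.

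**How far the rule could move a coefficient.** The documents give no durations, so the following are assumptions:

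- block duration normal, SD 5, 8 or 10 h;
- mean duration, shorter vs longer group: 18 vs 24, 20 vs 28 or 22 vs 34 h;
- 50% would have severe rebound pain in both groups (no true effect);
- onset = block end + an exponential delay with mean 1, 4, 8 or 12 h; event if onset is by 48 h.

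That gives 3 × 3 × 4 = 36 cases. Rule A counts unresolved blocks as non-events; rule B excludes them.

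| Mean durations | OR, rule A | OR, rule B | Largest log OR shift, A to B | Unresolved, longer-block group |
|---|---|---|---|---|
| 18 vs 24 h | 0.86–1.00 | 0.87–1.00 | 0.014 | 0–0.8% |
| 20 vs 28 h | 0.78–1.00 | 0.80–1.00 | 0.040 | 0–2.3% |
| 22 vs 34 h | 0.60–0.99 | 0.64–0.99 | 0.150 | 0.3–8.1% |

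The largest shift occurs at 22 vs 34 h, SD 10 h, mean delay 1 h:

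- Unresolved in the longer-block group: 1 - Φ((48 - 34)/10) = 1 - Φ(1.4) = 8.1%, or 51 of 635 patients. In the shorter: 1 - Φ(2.6) = 0.5%.
- Rule A: event probabilities 0.4968 and 0.4510; OR = (0.4510/0.5490)/(0.4968/0.5032) = 0.832.
- Rule B: divide by the resolved shares, 0.4968/0.9953 = 0.4991 and 0.4510/0.9192 = 0.4906; OR = 0.967.
- Shift: ln(0.967/0.832) = 0.150.

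**Yardstick.** With 1270 patients, half on dexamethasone and 50% events, each cell holds 1270/4 = 317.5, so the standard error of the log odds ratio is √(4/317.5) = 0.112. The shift exceeds this in 4 of the 36 cases, all at 22 vs 34 h with SD 10 h.

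**What drives the low odds ratios.** At 22 vs 34 h, SD 5 h and mean delay 12 h, the odds ratio is about 0.63 under rule A and 0.64 under rule B. That departure from 1 comes from the fixed 48 h window, which leaves less time after a long block. It is a property of a coherent target, risk within 48 h of block performance, and not of the coding rule.

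**The case for a change.** The best argument for a change is that a primary endpoint should be codable from the plan alone. This one omits a condition that the objective states, leaves open whether sensory or motor recovery marks resolution, and does not say which block counts if several were placed. The repair looks cheap: a few sentences, a count of unresolved blocks and one refit.

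The textual omissions are real. The rest is weaker.

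- An unresolved block is a non-event under the endpoint sentence only if no score of 7 or more is recorded. With such a score it is a literal event, so the two kinds of patient overlap.
- Pain before resolution has no frequency in the documents. The Exclusion wording about pain elsewhere concerns recovery-room patients who are already removed. If 5% had severe pain outside the block, 1.2–10.2% of the longer-block group would be classified differently, but the 5% is purely an assumption.
- The repair may cost more than it seems. Coding unresolved blocks as non-events requires telling them from unrecorded scores or resolution times, and nothing shows that the existing database can do this.
- A warning that the dexamethasone coefficient is not a treatment effect would answer a claim the plan does not make. It proposes a prediction model and a points score for estimating risk.

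**Conclusion.** No change to the plan is called for. The endpoint sentence leaves out a qualifier that its own name and the stated objective supply, and the plan is silent on an edge case. Analysts would sensibly require the severe score to follow resolution, and would count a block known to be unresolved at 48 h, with no score of 7 or more, as a non-event. No stated rule is shown to give a wrong result.

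The size is small or nil in most of the assumed settings: a log odds ratio shift of at most 0.014 or 0.040 in the two milder ones, and up to 0.150 in the most extreme, against a standard error of about 0.11. This rests on assumed durations, delays and a no-effect model. The plan reports only that some blocks exceed 24 h and mentions none beyond 48 h. If the recorded durations showed a material share of blocks beyond 48 h, the coding choice would deserve a line in the report. Sensory-block duration is already to be summarised, so that would be visible.
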